3.2 Study Population

At least 6 participants with SCD ages 18 to 60 years, inclusive will be enrolled (dosed) in this study. Participants in Part A (single dose) will be continued to Part B (multiple ascending-dose) based on SMC review of data. All eligible participants will proceed with the extended treatment period (Part C).

3.3 Evaluations at Screening and Check-in

Screening procedures will be conducted within 30 days prior to Day 1 dosing (Day -30 to Day -2). Screening and check-in evaluations for the single dose period each period are presented in [Table 3-1](#) and screening activities for Part C are found in [Table 3-4](#).

3.4 Randomization and Treatment Assignments

Participants will be enrolled sequentially into this open-label, fixed-sequence study. Randomization will not be performed in the study.

3.5 Determination of Sample Size

No sample size estimation was performed to determine the cohort size. The sample size is based on practical considerations, and not on a formal statistical power calculation. Six participants with SCD are expected to provide adequate characterization of PK and safety.

3.6 Study Drug Administration

GBT021601 will be administered orally. For the single-dose period, participants will fast at least 10 hours before and for at least 4 hours after study drug administration. Water will be allowed as desired except for 1 hour before and 1 hour after study drug administration.

Part A: Single oral dose of GBT021601 100 mg on Day 1.

Part B: The starting multiple ascending doses will be chosen to achieve ~20% to 30% Hb occupancy with once daily treatment (Dose 1) proceeded by loading doses. In addition, this dose level is predicted to achieve a Cmax at steady-state no higher than 2-fold the Cmax observed and well tolerated following single dose or multiple doses in study GBT021601-011. For the second dose level (Dose 2), the target of >30% Hb occupancy will be used as determined by the PK results found in GBT021601-011 and results from Part A of this study given at Weeks 8-13.

Part C: 300 mg loading dose twice daily over 4 days subsequent maintenance dose of 150 mg once daily starting from Day 5 and continuing through Week 6.

3.7 Concomitant Medications and Procedures

Study participants will be allowed to take other medications as needed as described in protocol. All concomitant medications will be documented.

In the interests of participant safety and acceptable standards of medical care the Investigator will be permitted to prescribe treatment(s) at his/her discretion. All treatments must be recorded in the participants' electronic case report form (eCRF) (medication, dose, treatment duration and indication) procedures along with start and stop date, type and reason for procedures will be captured on eCRF.

3.8 Drug Administration and Compliance

Study drug will be administered orally with approximately 240 mL non-carbonated room temperature water. Both tablets and capsules will be provided by sponsor.

Table 3-5: Identity of Study Drugs

Study Drug	Dosage Form	Dose
GBT021601	Tablet	100 mg
GBT021601	Capsule	5 mg, 25 mg

Study drug will be provided as a tablet or capsule as per below table:

Table 3-6: Study Drug for Extended Treatment Period

Study Drug	Dosage Form	Dose
GBT021601	Tablet	100 mg
GBT021601	Capsule	25 mg

The first dose of the study drug will be administered by delegated and trained staff at the CRU. A hand and mouth check will be performed to verify that the administered dose was swallowed.

For the Multiple Ascending-dose Period of this trial, at Week 8 and Week 13 Visits, the initial loading dose (as applicable) will be administered by delegated and trained staff at the CRU. Details regarding dosing, including the dose administered and the date and time of dosing, will be recorded.

For Extended Treatment Period of at least 6 weeks, loading dose will be 300 mg twice daily over 4 days and subsequent maintenance dose of 150 mg once daily starting from Part C Day 1 and continuing through Part C Week 6.

3.9 Evaluation of Efficacy

This section is not applicable for this study.

3.10 Evaluation of Pharmacokinetic Sampling Schedule

The PK samples for GBT021601 will be collected at time points specified in the PK/PD sampling schedules ([Table 3-1](#), [Table 3-2](#), [Table 3-3](#) and [Table 3-4](#)).

Single-dose Period: During the Single-dose Period, plasma and whole blood PK samples will be collected at the following times: Predose (within 60 minutes of dosing) and postdose at 0.25, 0.5, 1, 2, 4, 6, 8, 12 hours; 24 hours (Day 2), 36 hours, 48 hours (Day 3), and 72 hours (Day 4); Days 7, 14, 21, 28, and 42. The windows for sample collection are provided in table below:

Table 3-7: Windows for PK Sample Collection – Single-dose Period

Sample Collection Time	Allowed Deviation
0.0 – 1.0 hour	± 2 minutes

Sample Collection Time	Allowed Deviation
> 1.0 – 24.0 hours	± 5 minutes
> 24.0 – 72.0 hours	± 10 minutes
> 72.0 – 144.0 hours	± 15 minutes
> 144.0 hours	± 24 hours

Multiple Ascending-dose Period: Plasma and whole blood predose and postdose PK samples will be collected in the Multiple Ascending-dose period as listed in [below](#) table:

Table 3-8: PK and PD Sample Collection Times – Multiple Ascending-dose Period

Week	Predose ^a	Postdose
8	1 PK/PD sample Predose	1 PK/PD sample between 0.25 hour to 1 hour 1 PK/PD sample between 2 to 4 hours
9	1 PK/PD sample Predose	1 PK/PD sample between 0.25 hour to 1 hour 1 PK/PD sample between 2 to 4 hours
10	1 PK/PD sample Predose	1 PK/PD sample between 0.25 hour to 1 hour 1 PK/PD sample between 2 to 4 hours
11	1 PK/PD sample Predose	1 PK/PD sample between 0.25 hour to 1 hour, 1 PK/PD sample between 2 to 4 hours
12	1 PK/PD sample Predose	1 PK/PD sample between 0.25 hour to 1 hour 1 PK/PD sample between 2 to 4 hours
13	1 PK/PD sample Predose	1 PK/PD sample between 0.25 hour to 1 hour 1 PK/PD sample between 2 to 4 hours
14	1 PK/PD sample Predose	1 PK/PD sample between 0.25 hour to 1 hour 1 PK/PD sample between 2 to 4 hours
15	1 PK/PD sample Predose	1 PK/PD sample between 0.25 hour to 1 hour 1 PK/PD sample between 2 to 4 hours
16 EOT	1 PK/PD sample Predose	1 PK/PD sample between 0.25 hour to 1 hour 1 PK/PD sample between 2 to 4 hours
EOB/ET	Anytime during visit	

^a The pre-dose blood sample for PK and PD assessments should be collected within 30 minutes prior to dosing.

Table 3-9: PK and PD Sample Collection Times –Extended Treatment Period (Part C)

Extended Treatment Period		Pre-dose ^a	Postdose
Week	Day		
1	1	1 PK/PD sample	1 PK sample between 0.25 hour to 1 hour 1 PK/PD sample between 2 to 4 hours
2	15	1 PK/PD sample	1 PK sample between 0.25 hour to 1 hour 1 PK/PD sample between 2 to 4 hours

4	29	1 PK sample	1 PK sample at 4 hours
6	43	1 PK sample	1 PK sample between 0.25 hour to 1 hour 1 PK sample at 2 hours
10	71	1 PK sample	
14	98	1 PK sample	
Final Visit	Anytime during visit		

^a The pre-dose blood sample for PK and PD assessments should be collected within 30 minutes prior to dosing.

3.11 Evaluation of Pharmacodynamics Sampling Schedule

Single dose-period: Blood samples for hemoximetry, RBC deformability and dense cells will be collected at the same time as the PK samples (refer [Table 3-7](#)) at predose and 12 hours postdose on Day 1. In addition, hemoximetry samples will be collected on Days 2, 4, 7, 21, and 42.

Multiple ascending dose-period: Whole blood samples for hemoximetry, RBC deformability and dense cells will be collected at the same time as the PK samples (refer [Table 3-8](#)).

Extended Treatment Period: Whole blood samples for hemoximetry, RBC deformability and dense cells will be collected on Day 1 and Day 15 (refer [Table 3-9](#)).

CCI

3.12 Evaluation of Treatment Safety

3.12.1 Adverse Events

An adverse event (AE) is defined as any untoward medical occurrence associated with the use of a drug in humans, whether or not considered related to the study drug. An AE can therefore be any unfavorable and unintended sign, symptom, or disease temporally associated with the use of a study drug. A suspected adverse reaction is any AE for which there is a reasonable possibility that the drug caused the AE.

A treatment-emergent AE (TEAE) is an AE that occurs or worsens during the on-treatment period defined as the time from the first dose of study drug through minimum of 56 days + last dose of study treatment, date of study completion/discontinuation.

A Serious Adverse Event (SAE) is defined as any event that results in death, is immediately life threatening, requires inpatient hospitalization or prolongation of existing hospitalization, results in persistent or significant disability/incapacity, or is a congenital anomaly/birth defect or important medical events.

All AEs will be recorded from the time the study participant signs the Informed Consent Form (ICF) until the EOS Visit or ET Visit, whichever comes first. All AEs must be reported on the AE electronic case report form (eCRF) via the electronic data capture system. All serious and non-serious AEs must be followed until they are resolved or stabilized, or until reasonable attempts to determine resolution of the event are exhausted. Any participant who experiences an AE may be discontinued from study treatment at any time at the discretion of the Investigator. The Sponsor/Medical Monitor(s) must be notified of the study participant discontinuation.

The following details will be collected: description of the AE, onset date/time, action taken with study drug, outcome, severity (grade 1, grade 2, grade 3, grade 4 or grade 5), seriousness (yes, no) and relationship to study drug administration (not related or related).

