At the Week 13 Visit, eligible participants may be dose escalated to receive a loading dose and subsequent maintenance dose based on a predicted target of > 30% occupancy/modification. The mg dose and frequency will be determined by the PK results of GBT021601-011 and PK and hemoximetry results from Part A and Part B. Participants will receive maintenance doses through Week 16. Week 16 will be the end of treatment (EOT) Visit and participants will return to the clinical site for the end of Part B Safety Follow-up Visit approximately 5 half-lives (maximum of 120 days) after the final dose at the Week 16 Visit. The half-life will be determined from the PK results from the GBT021601-011 study and the PK results from Day 42 following the single dose (Part A) in this study. Participants will not be confined in the CRU during the Multiple Ascending-dose Period.

Extended Treatment Period (Part C)

As of Protocol Amendment 5, eligible participants may proceed with an Extended Treatment Period of at least 6 weeks, with a 300 mg loading dose twice daily over 4 days and subsequent maintenance dose of 150 mg once daily starting from Part C Day 1 and continuing through Part C Week 6. **CCI** [REDACTED]

Duration of Study Participation:

The maximum duration of the study is dependent on the half-life of GBT021601. At a minimum, the study duration will include a 28-day Screening period, an 8-week Single-dose Period, and a 6-week Multiple Ascending-dose Period for a total of 18 weeks. This will be followed by an EOB Visit 5 half-lives after the final dose of GBT021601. It is anticipated that 5 half-lives will not exceed 120 days after the final dose. Therefore, the maximum duration for a participant will be approximately 218 days or approximately 31 weeks.

As of Protocol Amendment 5, the maximum duration of the study will be approximately 53 Weeks, which includes the approximately 6-week Extended Treatment Period, and a 4- and 8-week follow up.

Number of Participants:

At least six (6) participants with SCD. Participants in Part A (single dose) will continue to Part B (multiple ascending-dose). As of Protocol Amendment 5, all eligible participants will proceed with the extended treatment period (Part C).

Participant Selection Criteria:

Participants with SCD ages 18 to 60 years, inclusive.

Test Product, Dose, Route of Administration, and Duration of Treatment:

Single-dose Period (Part A)

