^a HR, BP, RR, and body temperature will be measured after a participant has rested for at least 5 minutes in the supine position.

^b Window for collection: up to 3 hours predose, \pm 15 minutes up to 12 hours post, \pm 30 minutes if \geq 24 hours postdose.

^c ECGs (12-lead) will be collected in triplicate within 5 minutes after a participant has rested at least 5 minutes in the supine position. Pre-dose ECGs and vital signs on Day 1 may be performed within 3 hours prior to dosing.

^d Predose blood PK sample to be collected within 60 minutes prior to dosing. Postdose collection windows are: 0.25, 0.5 and 1 hour \pm 2 mins, 2 to 24 hours \pm 5 mins, 36 and 48 hours \pm 10 mins.

Table 3: Schedule of Assessments for Multiple Ascending-dose Period (Part B)

Study Week	Week 8 (Day 56 + 4 weeks) ^a	Week 9 (Day 63 ± 3 days)	Week 10 (Day 70 ± 3 days)	Week 11 (Day 77 + 3 days)	Week 12 (Day 84 ± 3 days)	Week 13 (Day 91 ± 3 days)	Week 14 (Day 98) ± 3 days	Week 15 (Day 105) ± 3 days	Week 16 (Day 112) EOT	Every 4 weeks through EOB ± 7 days	Day 218 (EOB/ET)
Physical examination	X					X			X		X
Height											
Weight	X		X								
Vital signs ^c	X	X	X	X	X	X	X	X	X		X
12-lead ECG (triple tracing) ^d	X					X			X		X
Study drug administration	X ^e	X	X	X	X	X ^f	X	X	X		
Dispense patient diary ^g	X	X	X	X	X	X	X	X			
Collect patient diary ^g		X	X	X	X	X	X	X	X		
Hematology and serum chemistry	X		X		X	X		X	X	X	X
Blood smear ^h	X								X		X
Serum erythropoietin	X					X	X		X		
eGFR ⁱ	X					X					X
Urinalysis	X					X					X
Pregnancy test (women only) ^j	X					X					
Pharmacokinetic assessment (whole blood and plasma) ^k	X	X	X	X	X	X	X	X	X	X	X

Study Week	Week 8 (Day 56 + 4 weeks) ^a	Week 9 (Day 63 ± 3 days)	Week 10 (Day 70 ± 3 days)	Week 11 (Day 77 + 3 days)	Week 12 (Day 84 ± 3 days)	Week 13 (Day 91 ± 3 days)	Week 14 (Day 98) ± 3 days	Week 15 (Day 105) ± 3 days	Week 16 (Day 112) EOT	Every 4 weeks through EOB ± 7 days	Day 218 (EOB/ET)
Hemoximetry ^k	X	X	X			X		X	X		X
RBC deformability, dense cells (if feasible) ^k	X	X	X			X		X	X		X
Concomitant medications	X	X	X	X	X	X	X		X		X
Adverse events	X	X	X	X	X	X	X		X		X
Clinic visit	X	X	X	X	X	X	X		X		X

Abbreviations: ECG, electrocardiogram; eGFR, estimated glomerular filtration rate; EOB, end of Part B; ET, early termination; RBC, red blood cell.

Note: For procedures scheduled to be performed at the same time, priority is to be given to collection of the PK samples at the designated time.

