ECGs, followed by vital signs, are to be taken before PK sampling unless PK samples will be late as a result

^a Week 8 (Day 56) is the first visit in the Multiple-Ascending-dose Period.

^b The Day 218 Visit will occur approximately 5 half-lives after the dose at Week 16.

^c HR, BP, RR, and body temperature will be measured after a participant has rested for at least 5 minutes in the supine position. Assessment of vital signs may be performed up to 3 hours predose.

^d 12-Lead ECG should be performed within 30 minutes prior to dose and will be collected in triplicate within 5 minutes after a participant has rested at least 5 minutes in the supine position.

^e Study drug will be administered as a loading dose of TBD mg and a maintenance dose of TBD mg every TBD (Dose 1) beginning at the Week 8 (Day 56) Visit. Participants will receive maintenance Dose 1 through Week 10. At the Week 8 Visit, the participant will remain in the clinic for 4 hours postdose for vitals, 12-lead ECG and AE assessment.

^f Study drug will be administered as a loading dose of TBD mg and a maintenance dose of TBD mg every TBD (Dose 2) beginning at the Week 13 (Day 91) Visit. Participants will receive maintenance Dose 2 through Week 16. At the Week 13 Visit, the participant will remain in the clinic for 4 hours postdose for vitals, 12-lead ECG and AE assessment

^g Site to dispense a new diary and collect the previous diary from the patient, when applicable. Diary to be collected only during the maintenance dosing when the participant is self-administering study drug at home. Participants should be instructed to complete the diary each week and return it at the next visit for site review.

^h A blood smear is to be performed before the Multiple Ascending Dosing Period Day 56 and Day 112 visits.

ⁱ The eGFR will be calculated using the Cockcroft-Gault formula.

^j A urine pregnancy test will be conducted. A serum pregnancy test will also be conducted when a positive urinary pregnancy test occurs for confirmation.

^k Samples for PK will be collected: predose, 0.25 to 1 hours postdose and 2 to 4 hours postdose. Sample collection times for hemoximetry and RBC deformability should be aligned with the predose PK sample and the 2 to 4 hour postdose PK sample. No 0.25 to 1 hour postdose sample shall be collected for hemoximetry or RBC deformability. The predose blood sample for PK and PD assessments should be collected within 30 minutes prior to dosing.

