10.5. Recording Adverse Events

10.5.1. General

All AEs will be recorded from the time the study participant signs the ICF form until the EOS Visit or ET Visit, whichever comes first. All AEs must be reported on the AE electronic case report form (eCRF) via the electronic data capture system. The Investigator is responsible for evaluating all AEs, obtaining supporting documents, and ensuring that documentation of the event is complete. Details of each reported AE must include at a minimum severity, relationship to study treatment, duration, and outcome. All serious and nonserious AEs must be followed until they are resolved or stabilized, or until reasonable attempts to determine resolution of the event are exhausted.

Any participant who experiences an AE may be discontinued from study treatment at any time at the discretion of the Investigator. The Sponsor/Medical Monitor(s) must be notified of the study participant discontinuation.

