At the Week 13 Visit, participants may be dose escalated to receive a loading dose and subsequent maintenance dose based on a predicted target of >30% occupancy/modification as determined by the PK results of GBT021601-011 and Part A of this study. Week 16 will be the end of treatment (EOT) Visit and participants will return to the clinical site for the end of Part B Safety Follow-up Visit approximately 5 half-lives after the final dose at Week 16. The elimination half-life will be determined from the PK results from the GBT021601-011 study and Day 42 following a single dose of 100 mg. It is anticipated that 5 half-lives will not exceed 120 days after the final dose.

Participants will not be confined at the CRU during the Multiple Dose Period.

Based on the findings from Dose Levels 1 and 2, there were no significant safety concerns related to GBT021601 and based on PK modeling, the planned doses for Part C are expected to result in Hb occupancy of approximately 54%.

Eligible participants may proceed with an Extended Treatment Period of at least 6 weeks, with a 300 mg loading dose twice daily over 4 days and subsequent maintenance dose of 150 mg once daily starting from Part C Day 1 and continuing through Part C Week 6. **CCI** [REDACTED] **CCI** [REDACTED]
[REDACTED]
[REDACTED]
[REDACTED]
[REDACTED]
[REDACTED]

The EOB Visit will occur after completion of the Multiple Ascending-dose Period as presented in [Table 3-3](#). The EOS Visit will occur after completion of the Extended Treatment Period as presented in [Table 3-4](#).

Figure 3-1: Study Schematic for GBT021601-012:

[figure not shown]

Table3-1: Schedule of Assessments for Single-dose Period (Part A)

	Screen n	Confinement					Outpatient				
		-1	1	2	3	4	7	14	21	28	42
Study Day	-30 to -2										
Informed consent	X										
Eligibility assessment	X	X									
Medical history ^a	X										
Physical examination ^b	X	X					X				
Height	X										
Weight	X	X					X	X	X	X	X
Vital signs ^c	X	X	X	X	X	X	X	X	X	X	X
12-lead ECG (triple tracing) ^d	X	X	X	X	X	X		X		X	
Study drug administration			X								
Serology (hepatitis A, B, C) HIV, SARS-CoV-2	X										
Alcohol (breath or blood) and urine drugs of abuse screen	X	X									
Hematology, Serum chemistry, and Lipid Panel ^e	X	X		X		X		X		X	
aPTT, INR, PT	X										
Serum erythropoietin		X	X			X		X		X	
SCD documentation or Hemoglobin Electrophoresis	X										
eGFR ^f	X	X									
Urinalysis	X	X				X					

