Note: For procedures scheduled to be performed at the same time, priority is to be given to collection of the PK samples at the designated time.

ECGs, followed by vital signs, are to be taken before PK sampling unless PK samples will be late as a result

^a Week 8 (Day 56) is the first visit in the Multiple-Ascending-dose Period.

^b The Day 218 Visit will occur approximately 5 half-lives after the dose at Week 16.

^c HR, BP, RR, and body temperature will be measured after a participant has rested for at least 5 minutes in the supine position. Assessment of vital signs may be performed up to 3 hours predose.

^d 12-Lead ECG should be performed within 30 minutes prior to dose and will be collected in triplicate within 5 minutes after a participant has rested at least 5 minutes in the supine position.

^e Study drug will be administered as a loading dose of TBD mg and a maintenance dose of TBD mg every TBD (Dose 1) beginning at the Week 8 (Day 56) Visit. Participants will receive maintenance Dose 1 through Week 12. At the Week 8 Visit, the participant will remain in the clinic for 4 hours postdose for vitals, 12-lead ECG and AE assessment.

^f Study drug will be administered as a loading dose of TBD mg and a maintenance dose of TBD mg every TBD (Dose 2) beginning at the Week 13 (Day 91) Visit. Participants will receive maintenance Dose 2 through Week 16. At the Week 13 Visit, the participant will remain in the clinic for 4 hours postdose for vitals, 12-lead ECG and AE assessment

^g Site to dispense a new diary and collect the previous diary from the patient, when applicable. Diary to be collected only during the maintenance dosing when the participant is self-administering study drug at home. Participants should be instructed to complete the diary each week and return it at the next visit for site review.

^h A blood smear is to be performed before the Multiple Ascending Dosing Period Day 56 and Day 112 visits.

ⁱ The eGFR will be calculated using the Cockcroft-Gault formula.

^j A urine pregnancy test will be conducted. A serum pregnancy test will also be conducted when a positive urinary pregnancy test occurs for confirmation.

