7.17.1 Adverse Events

All AE summaries will include treatment emergent AEs and will be presented for SCD related and SCD non-related separately.

SCD related AEs include:

SCD-related AEs comprise the following PTs: sickle cell anemia with crisis, ACS, pneumonia grouped terms (includes all PTs of pneumonia reported in this study), priapism, and osteonecrosis.

All AEs will be coded by primary system organ class (SOC) and preferred term (PT) according to the MedDRA Version 24.0 or higher and presented by participant in data listings.

The overall incidence of TEAEs (number of events, number and percentage of participants) will be summarized parts and overall. It includes: AEs, TEAEs, TEAEs by severity, SAEs, causally related TEAEs and SAEs, TEAEs leading to study or treatment discontinuation, life-threatening SAEs, and SAEs resulting in death.

The TEAEs will be summarized and tabulated at both the participant (n [%] of participants) and event (number of events) level:

- TEAEs by SOC and PT
- TEAEs by SOC, PT and maximum reported severity
- TEAEs by SOC, PT and closest relationship to study drug
- TEAEs by SOC, PT

For the incidence at the participant level by SOC and PT, if a participant experiences more than 1 event within the same SOC and PT, only 1 occurrence will be included in the incidence.

For the incidence at the participant level by SOC, PT, and severity, if a participant experiences more than 1 event within the same SOC and PT, only the most severe occurrence will be included in the incidence.

For the incidence at the participant level by SOC, PT, and relationship, if a participant experiences more than 1 event within the same SOC and PT, only the closest relationship will be included in the incidence.

Any SAEs, AEs with outcome of death, or AEs resulting in discontinuation of study or study drug will be listed separately.

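### For a participant who completes Part B and does not enter Part C, the TEAE window closes on Day 168 and leaves 50 of 106 follow-up days out of the SOC/PT, severity and relationship tables

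*SAP*

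**What the plan says.** **Window.** SAP 3.12.1 defines a TEAE as an AE that starts or worsens from first dose "through minimum of 56 days + last dose of study treatment, date of study completion/discontinuation". The clock is tied to study treatment as a whole, and no part-specific version is given.

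**Dosing and follow-up in Part B.** SAP Table 3-3, footnote f: "Participants will receive maintenance Dose 2 through Week 16". The Protocol Table 3 column is "Week 16 (Day 112) EOT". Footnote b of the same table: "The Day 218 Visit will occur approximately 5 half-lives after the dose at Week 16". The Protocol synopsis puts this visit at "approximately 5 half-lives (maximum of 120 days) after the final dose at the Week 16 Visit". SAP 3.1 adds: "It is anticipated that 5 half-lives will not exceed 120 days after the final dose".

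**AE collection.** Protocol 10.5.1: "All AEs will be recorded from the time the study participant signs the ICF form until the EOS Visit or ET Visit", whichever is first. Protocol Table 3 marks AE assessment at the Day 218 visit. Protocol 4.3.2 calls that visit the end-of-study visit; the synopsis calls it end of Part B.

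**Reporting.** SAP 7.17.1: "All AE summaries will include treatment emergent AEs". The detailed tables (SOC/PT, severity, relationship) are TEAE tables. The overall incidence table also has AE and SAE lines. All AEs are listed by participant, and SAEs, deaths and discontinuations are listed separately.

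**Part C.** All eligible participants proceed (Protocol 4.4), but Protocol Table 4 requires consent and eligibility confirmation, and Protocol 5.2.1 adds nine exclusions (numbers 28 to 36). Dosing runs through at least Day 42. The last dated visit is Week 14 (Day 98), followed by an undated Final Visit.

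**The concern.** Safety and tolerability are the primary objective. The protocol follows participants for about five half-lives after Part B and collects AEs to that visit, yet the tables that describe AEs by type, severity and relatedness can stop at 56 days. Laboratory values have no such limit: SAP 7.17.2 summarises them by visit, and hematology and chemistry continue every 4 weeks through the EOB visit. The same late period could therefore appear in the laboratory summaries and not in the TEAE tables.

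With six participants, one participant is 1/6 = 16.7 percentage points of an incidence, so a single late event can matter. It changes a row only if that participant did not already have the same preferred term inside the window.

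**Working it through.** **1. The protocol's own Day 218.** The synopsis gives an 8-week Part A, a 6-week Part B and at most 120 days of follow-up: 56 + 42 + 120 = 218 days, and 218/7 = 31.1 weeks. Both match the stated figures. Table 3, however, doses to Day 112, so Day 218 is 218 − 112 = 106 days after the last scheduled dose, and the 120-day cap would fall on Day 112 + 120 = Day 232. These passages need reconciling; both cases are carried below.

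**2. Participant who completes Part B and does not enter Part C.**
- Window closes: 112 + 56 = Day 168.
- Follow-up to Day 218: 218 − 168 = 50 days outside; 50/106 = 47.2%.
- Follow-up to Day 232: 232 − 168 = 64 days outside; 64/120 = 53.3%.

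**3. Participant who enters Part C, window applied across the whole study.** The last dose of study treatment is now in Part C, so all of Part B follow-up lies between first dose and last dose + 56 days: 0 of 106 days outside. The window closes on Part C Day 42 + 56 = Day 98, the nominal Week 14 visit (±3 days). Only time between then and the Final Visit could fall outside.

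The protocol's maximum duration can be rebuilt with no time after Day 98: 28 (screening) + 218 + 28 (Part C screening) + 42 + 56 = 372 days, and 372/7 = 53.1 weeks, against the stated 53.

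**4. Participant who terminates early.** The ET visit is at discontinuation (Protocol 4.6) and AE recording stops there, so the 56-day limit removes nothing.

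**5. Dependence on the half-life.** The documents give no value, so it is an assumption. If follow-up is five half-lives of length t days, the excluded share is max(0, 5t − 56)/(5t). The drug remaining at day 56, assuming simple exponential decline, is 2^(−56/t).

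| t (days) | 5t (days) | Days outside | Share outside | Drug remaining at day 56 |
|---|---|---|---|---|
| 11.2 | 56 | 0 | 0% | 3.1% |
| 15 | 75 | 19 | 25.3% | 7.5% |
| 20 | 100 | 44 | 44.0% | 14.4% |
| 21.2 (= 106/5) | 106 | 50 | 47.2% | 16.0% |
| 24 (= 120/5) | 120 | 64 | 53.3% | 19.8% |

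The calendar result in step 2 needs only the scheduled days. The half-life matters if the visit is moved to track it, and for judging how much exposure remains.

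**6. Consistency within the SAP.** SAP 7.3, on incomplete AE dates, treats an AE as pre-treatment if it ended before first dose and otherwise as a TEAE, with no upper limit. A late, incompletely dated event can be a TEAE under 7.3 and not under 3.12.1.

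**The case against.** The strongest reply is that the planned path avoids the problem. The clock follows the last dose of study treatment, all eligible participants are to enter Part C, and for them no Part B follow-up is lost. The 56 days equal the 8-week Part C follow-up, and the revision history of SAP version 3.0 records an update of the TEAE definition, so the choice may be deliberate. Early terminators lose nothing. This all stands, and it confines the loss to people who finish Part B follow-up and do not continue. The documents do not count them. But with further consent and nine further exclusions, the SAP should provide for them.

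A reader might also infer that every AE table drops these events. It does not follow: the overall AE and SAE lines and the listings are not limited to TEAEs, and in a study of about six participants the listings carry much of the safety review.

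The wording is itself loose. A comma joins the two end points, and the minimum could be taken to mean at least 56 days, in which case the window need not close there. The earlier-of reading is the more natural one. The SAP also analyses the parts separately without saying whether the window runs per part or per study. Applied per part, every Part B participant would lose Days 169 to 218. The text does not state that rule, so that loss cannot be asserted.

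Finally, a longer window in a single-arm descriptive study counts more background sickle cell events as TEAEs. That is a fair cost, partly offset by the SAP's separate SCD-related and non-SCD-related presentation.

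**Conclusion.** The point holds in a limited form. For a participant who completes Part B and does not enter Part C, the TEAE tables by SOC/PT, severity and relationship omit 50 of 106 follow-up days (47%), or 64 of 120 (53%) at the cap. This rests on the earlier-of reading of SAP 3.12.1 and a last dose on Day 112.

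Three stronger readings are not supported:
- **Nearly half of follow-up is lost for all participants.** On a whole-study window, Part C entrants lose none of their Part B follow-up.
- **Part C follow-up is cut short.** The Final Visit is undated, and the stated follow-up ends 8 weeks after Day 42. Events after nominal Day 98 could be missed; whether any such period exists is not shown.
- **Incidence is biased downward by events on substantial drug levels.** No half-life, late event rate or number of affected participants is given. The 16% to 20% remaining at day 56 is what a half-life of 21 to 24 days would imply, and at 11.2 days or less a five-half-life follow-up loses nothing.

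**What to change.** - In SAP 3.12.1, define the TEAE period as first dose through the EOB visit for participants not entering Part C, or through the EOS/ET visit for Part C or early termination.
- State that it applies across the whole study, with each event assigned to the part in which it starts.
- Flag events that start more than 56 days after the last dose, so that the shorter window can still be read off.
- Give the incomplete-date rule in SAP 7.3 the same end point.

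The cost is a few SAP sentences and a flag variable; the data are already collected. The downside is that a few more background SCD events will count as TEAEs.
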